11.4.1 Primary Analysis (Safety)

Incidence Rate of Events

The primary outcome for this study will be the combined number and incidence rate of several arrhythmias of interest for 14 days post-study drug. The combined number of arrhythmic events in each treatment group will be calculated along with the arrhythmia incidence rate defined as the number of arrhythmia events of interest divided by the total person-time within each treatment group (or the overall FDY-5301 group), expressed as a percentage. The summarization will be presented by 2 separate periods within the 14-day monitoring duration, and also as overall. Period 1 will be the first 48 hours since the start of PCI and period 2 will be the remaining time of 14-day monitoring duration.

The same summarization method will be repeated after stratification of baseline TIMI flow (grade 1 and lower combined, or, grade 2 and 3 combined) and infarct type (anterior or other).

Person-time is an estimate of the time-at-risk in hours for all patients who contributed to the analysis population. The total person-time is calculated as the sum of recording time across patients during the 14 day monitoring period, within each treatment group (or the overall FDY-5301 group). The unit for person-time in this study is person-hours.

The number of arrhythmias of interest and its incidence rates will be summarized by treatment group and the overall FDY-5301 group.

The incidence rate ratio of each active treatment group (and overall) against the placebo group will be calculated.

As an exploratory sub-analysis, the summarization for the number of events and incidence rates will be repeated separately for each arrhythmia category as outlined in Section 6.1 and also separately for non-serious arrhythmias (ie, any arrhythmias which do not meet the criteria as outlined in Section 6.1).

The arrhythmia incidence rates (ie, arrhythmias per person-time) for each arrhythmia type will be summarized by treatment groups in hourly intervals. The intervals may be altered upon reviewing the actual data. Arrhythmia rates by time interval may also be presented in a graphical format.

Occurrence of reperfusion arrhythmias collected prior to use of the continuous rhythm monitoring device will be summarized according to categories as defined in the CRF.

Relationship between each arrhythmia type occurred within 48 hours of the start of PCI procedure and all-cause mortality may be evaluated depending on data availability.

Time-to-Last-Event

The time-to-last-event is defined as the duration between the start time of PCI and the last occurrence of the arrhythmia event. The time-to-event will be censored for a subject if a subject does not experience any arrhythmias of interest before the end of the 14-day monitoring period or the date of early termination from the study. The censoring time will be at the last available time of arrhythmia monitoring.

Median and first and third quartiles of the time-to-last-event will be summarized for each treatment group and the overall FDY-5301 group for each arrhythmia of interest (and combined).

Kaplan-Meier curves will be presented by treatment, baseline TIMI flow, and infarct type for each arrhythmia of interest and also repeated separately for each arrhythmia category.

Time-to-Patch-Application

The duration between the start of PCI to the application of the patch will be derived and summarized by treatment group.

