4.1 Primary Outcome

The primary outcome for this study will be the combined number and incidence rate of several arrhythmias of interest that occur in each group over a 14 day period post-study drug. These arrhythmias including ventricular fibrillation, sustained ventricular tachycardia (≥ 125 BPM, ≥ 30 seconds), non-sustained ventricular tachycardia (≥ 125 BPM, ≥ 16 beats, < 30 seconds) and high degree AV block (2nd or 3rd degree, ≥ 8 beats) were chosen because they are significant prognostic indicators of depressed left ventricular ejection fraction and cardiac death [1]. The combined number of arrhythmic events in each group will be calculated along with the arrhythmia incidence rate defined as the percentage of patients in each group experiencing at least one of the defined arrhythmias of interest.

An exploratory sub-analysis will be conducted to determine the number and incidence rate of each separate arrhythmia type per dose group.

Continuous cardiac monitoring will occur for 14 days post PCI by means of wearable patch devices.

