14.1.3 Study Outcomes

The primary outcome for this study will be the combined number and incidence rate of several arrhythmias of interest that occur in each group over a 14 day period post-study drug. These arrhythmias including ventricular fibrillation, sustained ventricular tachycardia (≥ 125 BPM, ≥ 30 seconds), non-sustained ventricular tachycardia (≥ 125 BPM, ≥ 16 beats, < 30 seconds) and high degree AV block (2nd or 3rd degree, ≥ 8 beats) were chosen because they are significant

prognostic indicators of depressed left ventricular ejection fraction and cardiac death [1]. The combined number of arrhythmic events in each group will be calculated along with the arrhythmia incidence rate defined as the percentage of patients in each group experiencing at least one of the defined arrhythmias of interest.

An exploratory sub-analysis will be conducted to determine the number and incidence rate of each separate arrhythmia type per dose group.

Secondary exploratory efficacy outcomes will include:

Infarct size as a proportion of ventricular volume (INF/VV), the myocardial salvage index (MSI), absolute MI size (INF) at 72 +/- 24 hours and 3 months post study drug measured by CMR.

The proportion of patients with ST-segment resolution at 4 hours post study drug.

Serum levels of troponin calculated as AUC 0-48 hours post study drug.

Cardiac-related adverse events including the development of heart failure.

The incidence of all-cause and cardiac mortality out to 6 months post PCI.

In addition to the measurement of safety and efficacy parameters in this study, serum biomarker levels of cardiac injury, inflammation and remodeling will also be assessed.

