14.1.4 Sample Size Estimation

Little data exists on the incidence of arrhythmias that occur over an extended period of time following AMI and monitoring strategies for this type of assessment have not been optimized in a clinical trial setting. The primary goal of our study is to characterize the occurrence of arrhythmias in this patient population for 14 days post-AMI and to determine the feasibility of using ambulatory patch ECG monitors to capture this data. These data should be regarded as exploratory with the objective of identifying a meaningful clinical end point that can be easily measured in future, pivotal studies that are adequately powered to detect differences across treatment groups.

Estimating a drop-out rate of approximately 50%, we will need to enroll up to 160 patients in order to obtain a final total sample size of 80 patients. A final sample size of 80 patients will provide 80% power to detect a 37% reduction in INF/VV assuming an SD of 10%, a 24% increase in MSI assuming an SD of 20% and a 39% reduction in Troponin AUC with an SD of 60%. Equal variance was assumed among groups with an unbalanced allocation of patients to placebo (n=20) and combined FDY-5301 treatment groups (n=60).

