14.1.6 General Analysis of Safety and Efficacy Outcomes

Analysis of the primary safety outcome: characterize the number and incidence rate of serious arrhythmias that occur during a 14-day interval in this patient population. No hypothesis will be tested and data will be descriptive in nature only. A more detailed analysis strategy will be outlined in the SAP.

Analysis of exploratory secondary efficacy outcomes: For all variables with a continuous outcome including infarct size relative to the VV, MSI, absolute MI size, cardiac function, biomarkers of cardiac injury and cardiac troponin levels, a single pairwise comparison to analyze differences between all three FDY-5301 groups (combined) and placebo will be used. An unpaired Student's T test will be used for the pairwise comparison if the data are normally distributed and a Mann-Whitney rank test will be used for nonparametric data. Each group will then be tested using a one-way analysis of variance (ANOVA) to obtain a common variance followed by a Dunnett's post-test to separately compare each FDY-5301 dose group to placebo.

For categorical outcome including ST-segment resolution and incidence of all-cause and cardiac related mortality or morbidity, odds ratios comparing each FDY-5301 treatment group with placebo will be calculated.

Physical examination data from baseline, post-study and **medical history** data at baseline and peri-procedural arrhythmia data will be listed by patient. All clinical safety and tolerability data will be listed for each subject. **Laboratory values** will be calculated as group mean data and presented in shift tables. Comments as to the clinical significance of out of range values will be listed separately. **Adverse event** data will be summarized by group, visit, severity, and possible relationship to the study drug.

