11.4.3 Exploratory Analysis (Safety)

Incidence Rate of New Onset Atrial Fibrillation

The exploratory outcome for this study will be the combined number and incidence rate of new onset atrial fibrillation for 14 days post-study drug. The combined number of events in each treatment group will be calculated along with incidence rate defined as the number of events divided by the total person-time within each treatment group (or the overall FDY-5301 group), expressed as a percentage.

The number of new onset atrial fibrillation and new onset atrial fibrillation incidence rates will be summarized by treatment group and the overall FDY-5301 group.

The incidence rate ratio of each active treatment group (and overall) against the placebo group will be calculated.

The summarization will be presented by 2 separate periods within the 14-day monitoring duration, and also as overall. Period 1 will be the first 48 hours since the start of PCI procedure and period 2 will be the remaining time of 14-day monitoring duration.

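### SAP 11.4.1 replaces the protocol's primary patient percentage with an event rate per person-hour labelled as a percentage, and SAP 13 does not say that the patient measure is dropped

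*SAP*

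**What the plan says.** Protocol section 4.1 gives the primary outcome two components: the combined number of arrhythmic events per group, and an "arrhythmia incidence rate defined as the percentage of patients in each group experiencing at least one of the defined arrhythmias of interest". The Synopsis, section 11 and section 14.1.3 repeat the definition; in 14.1.3 the second component is again "the percentage of patients in each group experiencing at least one of the defined arrhythmias of interest".

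SAP section 11.4.1 keeps the event count. It gives the arrhythmia incidence rate a new definition, "number of arrhythmia events of interest divided by the total person-time within each treatment group (or the overall FDY-5301 group), expressed as a percentage", and adds: "The unit for person-time in this study is person-hours". It also plans rate ratios of each active group, and of the active groups together, against placebo. Section 11.4.3 defines the rate of new-onset atrial fibrillation the same way: "number of events divided by the total person-time within each treatment group (or the overall FDY-5301 group), expressed as a percentage".

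SAP section 13 lists the person-time formula as a change from the protocol and explains it as an adjustment for monitoring time lost to withdrawal, device failure or death. It does not mention the patient percentage. SAP section 4 commits to identifying substantial differences from the protocol.

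**The concern.** The two documents give one name to two different quantities. The protocol's is a proportion of patients. The SAP's is a rate with a time unit that counts repeat events, so it is not a percentage of anything. A reader who knows the protocol will take the SAP's percent sign to mean patients affected.

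The protocol's event count was always open to domination by one patient with many runs of tachycardia. The patient percentage was the component that could not be, and it is the one removed. The count, the rate and the rate ratio that remain are all event-weighted.

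The primary data are meant to help with "identifying a meaningful clinical end point that can be easily measured in future, pivotal studies", and anyone planning such a study needs the share of patients affected. Because the protocol also says "No hypothesis will be tested and data will be descriptive in nature only", the reported summaries are themselves the primary result.

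**Working it through.** The documents state no expected arrhythmia rate, so there is no planned figure to reproduce. The event numbers below are assumptions chosen to show how the two measures behave.

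**Inputs.** Monitoring lasts 14 days (protocol 4.1), so a fully recorded patient gives 14 × 24 = 336 hours. Planned evaluable groups are 20 placebo and 60 combined active (protocol 14.1.4). The SAP allocates 1:1:1:1 (section 7), so up to 160 randomized patients means 160/4 = 40 per arm.

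**Formulas.** Protocol measure = 100 × patients with at least one event / n. SAP measure = 100 × events / person-hours.

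**1. Scale.** Each affected patient has one event.
- n = 20: 20 × 336 = 6,720 person-hours. Five affected patients give 5/20 = 25% (exact 95% CI 8.7% to 49.1%) under the protocol and 5/6,720 = 0.074% under the SAP.
- n = 40: 40 × 336 = 13,440 person-hours. Ten affected patients give 10/40 = 25% (12.7% to 41.2%) and 10/13,440 = 0.074%.

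**2. The rate does not determine the share.** With n = 20, let 20 events fall in 1, 10 or 20 patients. The protocol measure is 5%, 50% or 100%. The SAP measure is 20/6,720 = 0.298% each time.

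**3. One patient.** Both arms have 25% affected, equal recording time and one event per affected patient, except for one patient in one arm.

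| Runs in that patient | Rate ratio, 20 per arm | Rate ratio, 40 per arm |
|---|---|---|
| 5 | 9/5 = 1.8 | 14/10 = 1.4 |
| 10 | 14/5 = 2.8 | 19/10 = 1.9 |
| 30 | 34/5 = 6.8 | 39/10 = 3.9 |

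**4. Opposite order.** Suppose 30 of 60 active patients have one event each and 2 of 20 placebo patients have ten each. The protocol measure is 50% against 10%, a ratio of 5.0. The SAP measure is 30/20,160 = 0.149% against 20/6,720 = 0.298%, a rate ratio of 0.5.

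**5. Whether other SAP outputs supply the patient share.**
- The Kaplan-Meier curves in 11.4.1 come closest, but "The time-to-last-event is defined as the duration between the start time of PCI and the last occurrence of the arrhythmia event". An affected patient is therefore counted late, after event-free patients with short recordings have left the risk set. Take 5 of 20 affected, with first event on day 1 and last on day 13. With complete recording the curve ends at 5/20 = 25%. If 5 event-free patients stop recording at day 3, it ends at 5/15 = 33%; if 10 stop, at 5/10 = 50%. Time to first event gives 5/20 = 25% throughout.
- The adverse event tables (SAP 11.5.1) count patients by MedDRA term, not for the centrally read composite of four arrhythmias over 14 days.
- Persistent arrhythmias (SAP 11.4.2.3) are read from 12-lead ECGs at 30 days and 3 months, which is a different outcome.

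**The case against.** The strongest reply is that the change is disclosed and has a sound reason. SAP 13 gives the formula under a heading for changes from the protocol, the SAP declares that it supersedes the protocol's statistics, and redefining a named quantity implies replacing it. The formula is indeed disclosed. But lost recording time is a reason to add a rate; it does not explain why the patient measure goes unreported.

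Two points about documents limit the finding. The table shells are separate and were not available, so a patient-count row may exist there; the finding concerns the SAP text, which plans none and itself prescribes the percentage label. The SAP also cites protocol versions of 2 April and 21 August 2017, whereas the protocol reviewed is dated 30 August 2017. SAP 13 nevertheless treats person-time as a departure from the protocol.

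The Kaplan-Meier example depends on its timing. If first events also fell after day 3, a first-event curve would end at the same 33% and 50%, and the crude 25% would ignore unobserved time. That is fair. The example shows that the last-event curve can depart from the patient share, not that it must, and it is a reason to show a first-event estimate beside the crude percentage.

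Finally, exact intervals and a first-event curve go beyond what the protocol promised. The minimum repair is the patient count and percentage, a corrected label and a sentence in section 13. The additions are inexpensive and help in reading small groups with incomplete recording.

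**Conclusion.** The concern holds. Followed as written, the SAP omits one of the protocol's two primary summaries and attaches its name and a percent sign to a different quantity. Section 13 discloses the new formula but not the omission.

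The gap between the measures is large under plausible patterns: 25% against 0.074% in the simplest case, rate ratios of 1.4 to 6.8 produced by a single patient when the shares affected are equal, and a possible reversal of group order. These sizes rest on assumed event counts and, apart from the Kaplan-Meier example, on full or equal recording; the conclusion about the text does not. No hypothesis test, error rate or power is affected, and patient-level information is reduced rather than wholly absent. The point should be fixed before database lock because it concerns what the trial reports as its primary result.

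**What to change.** - **SAP 11.4.1:** reinstate the number and percentage of patients with at least one arrhythmia of interest over 14 days, for each arm and for overall FDY-5301, with exact 95% confidence intervals. Add a Kaplan-Meier estimate of time to first event to handle truncated recordings.
- **Rate:** keep it as a companion measure, labelled as events per 100 person-hours or per 100 person-days, not as a percentage. In the first example, five events over 20 × 14 = 280 person-days is 1.79 per 100 person-days. If an interval is given for the rate ratio, use a method that allows for repeated events within a patient.
- **SAP 11.4.3:** correct the percentage label only.
- **SAP 13:** state that both the patient percentage and the event rate are reported, and why the rate was added.

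The cost is SAP wording and a few table rows. No new data are needed.

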11.4.2.2 Proportion of Patients with ST-segment Resolution at 4 hours Post-study Drug

12-lead ECGs will be used to obtain baseline ST-segment elevation prior to treatment in order to evaluate ST-segment resolution 4 hours post-study drug.

ST-segment resolution will be defined as a reduction of the ST-segment elevation by 50% when compared to the baseline. Evaluation of the percentage of ST-segment resolution will be undertaken on the single worst ECG lead (defined as the lead with the maximal ST-segment elevation). Baseline is defined as the maximal ST-segment elevation obtained at Day 1 screening. Results will be categorized as either resolved or non-resolved.

The number of patients with ST-segment resolution will be tabulated by treatment group. Odds ratios will be calculated for each FDY-5301 treatment group (and overall) against the placebo group, along with its 95% confidence interval.

The same summarization method and statistical analyses will be repeated by baseline TIMI flow (grade 1 and lower, or, grade 2 and 3) and infarct type (anterior or other).

Clinician's ECG interpretation collected from the eCRFs will be listed.

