13 CHANGES FROM THE PROTOCOL SPECIFIED STATISTICAL ANALYSES

For the analysis of arrhythmias of interest, a person-time adjustment will be applied to account for potential missing data during the 14-day monitoring period, due to possible unforeseen reasons such as patient withdrawal, device failure or death. The incidence rate for each treatment group (and overall FDY-5301) will be calculated as the number of events divided by the total person-time of monitoring within each treatment group. The incidence rate ratios of each treatment group (and overall FDY-5301) versus the placebo will be derived.

Scope of the interim analyses has been updated.

Overall summary for primary and exploratory safety and efficacy endpoints will be summarized by stratification of TIMI flow grade and infarct location

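### The primary arrhythmia rate ratio pools repeat events over person-hours with no interval and no per-patient view, so one patient can drive it

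*SAP*

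**What the plan says.** Protocol 4.1, 11 and 14.1.3 ask for two things on the primary outcome: the combined number of arrhythmic events in each group, and an incidence rate, which is "the percentage of patients in each group experiencing at least one of the defined arrhythmias of interest".

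SAP 11.4.1 keeps the event count but changes the rate, now "defined as the number of arrhythmia events of interest divided by the total person-time within each treatment group". On the denominator: "The total person-time is calculated as the sum of recording time across patients during the 14 day monitoring period". Arms are then compared: "The incidence rate ratio of each active treatment group (and overall) against the placebo group will be calculated". SAP 13 declares the change and repeats the contrast: "The incidence rate ratios of each treatment group (and overall FDY-5301) versus the placebo will be derived". Its stated reason is incomplete monitoring: "a person-time adjustment will be applied to account for potential missing data during the 14-day monitoring period". Repeat events within a patient are not mentioned.

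Neither section names an interval, a standard error, a dispersion estimate or a rule for repeat events. SAP 11.4.3 uses the same construction for new-onset atrial fibrillation. By contrast, SAP 11.4.2.2 says: "Odds ratios will be calculated for each FDY-5301 treatment group (and overall) against the placebo group, along with its 95% confidence interval". SAP 11.4.2.3 does the same for persistent arrhythmias.

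Protocol 14.1.6 makes the primary analysis descriptive, with no hypothesis test. Protocol 14.1.4 calls the data exploratory, "with the objective of identifying a meaningful clinical end point that can be easily measured in future, pivotal studies".

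**The concern.** Runs of non-sustained ventricular tachycardia can recur many times in one patient. A pooled count gives that patient as many votes as he or she has runs. In arms of about 20, one or two such patients can set the arm's rate, and a ratio printed alone does not let the reader see this.

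Two things are at stake. This is the first study in patients and safety is its stated focus, so a chance ratio well above or below 1 could be read as harm or protection. The protocol also wants these data to guide a pivotal endpoint. Sizing a trial on a recurrent-event rate needs the between-patient dispersion, and the SAP text plans no estimate of it.

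**Working it through.** **Inputs from the documents.** 80 evaluable patients, 20 placebo and 60 active (Protocol 14.1.4); 1:1:1:1 allocation (SAP 7); up to 160 enrolled at about 50% drop-out (Protocol 14.1.4); 14 days of monitoring, or 14 × 24 = 336 hours if complete; ITT analysis repeated in the per-protocol set (SAP 11.4).

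**The plan's own figure.** 80 / (1 − 0.5) = 160, reproduced. So the arms hold about 20 evaluable patients each, and up to 160 / 4 = 40 in the ITT set. The plan gives no rate, standard error or power for the arrhythmia ratio, so there is nothing further to reproduce.

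**One patient's leverage.** Rate ratio = (events / hours, active) ÷ (events / hours, placebo). With complete recording, 20 patients give 20 × 336 = 6,720 hours. Let 4 of 20 be affected in each arm, so the patient risk ratio is 1.0. Each affected patient has one event except as stated.

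| Case | Events | Rate ratio |
|---|---|---|
| One active patient has 5 runs | 8 vs 4 | 2.0 |
| One active patient has 10 runs | 13 vs 4 | 3.25 |
| One active patient has 20 runs | 23 vs 4 | 5.75 |
| Two active patients have 10 runs each | 22 vs 4 | 5.5 |
| One placebo patient has 10 runs; 12 of 60 affected in combined active | 12/60 vs 13/20 | 0.20 / 0.65 = 0.31 |

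**What an interval would show.** Patient-level variance of the log ratio: for each arm, Σ(xᵢ − x̄)² / (Σxᵢ)² × n/(n − 1), then add the two arms.

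- Ratio 3.25. Active: 94.55 / 169 × 20/19 = 0.589. Placebo: 3.2 / 16 × 20/19 = 0.211. SE = √0.799 = 0.894. Interval 3.25 × exp(±1.96 × 0.894) = 0.56 to 18.7.
- Ratio 0.31. Placebo: 0.589. Active: 9.6 / 144 × 60/59 = 0.068. SE = √0.657 = 0.810. Interval 0.06 to 1.51.
- An exact Poisson interval that treats events as independent gives 1.004 to 13.7 and 0.13 to 0.73. Both exclude 1, so a plain Poisson interval would make matters worse.

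**How often chance alone gives a large ratio.** The documents give no event rates, so these are assumptions: negative binomial counts, no drug effect, mean 1 to 2 events per patient, 20-40% of patients with any event, 40,000 simulated trials per scenario.

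| Patients compared | Ratio outside 0.5 to 2 |
|---|---|
| 60 vs 20 (overall vs placebo) | about 16-54% |
| 20 vs 20 (one dose vs placebo) | about 24-62% |
| 120 vs 40 | about 5-37% |
| 40 vs 40 | about 10-46% |

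The low end is mean 1 with 40% affected; the high end is mean 2 with 20% affected.

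**How much is clustering and how much is small numbers.** A second null model fixed 20% affected at 20 per arm and varied the repeats. One dose's ratio was at least 2 or at most 0.5 in 38% of trials with no repeats, 48% with a geometric number of runs (mean 3), and 58% with a heavy-tailed number. For overall vs placebo the figures were 22%, 36% and 49%. With repeats, the top patient supplied 31-40% of the two arms' events, and removing that patient cancelled 51-58% of the extreme single-dose ratios.

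**Choice of interval.** In that second model, over 10-30% affected and 20 or 40 per arm, a nominal 5% comparison of one dose with placebo rejected in 23-49% of null trials with repeats if events were treated as independent. It rejected in 5-14% with the patient-level sandwich interval, and in 0.2-4.7% with a patient-level permutation test. A percentile patient bootstrap under the negative binomial model covered about 84-92%, with an infinite upper limit in about 40% of trials at 20% affected. The last figure can be checked. With three or fewer affected placebo patients, a resample contains none with probability at least (17/20)²⁰ = 3.9%, above 2.5%. The chance of three or fewer affected among 20 at 20% is 41%.

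**The case against.** The strongest reply is that the primary analysis is descriptive by design. No hypothesis is tested, no stopping rule or decision uses the ratio, and no error rate is broken. That stands, and it limits the severity. It does not argue against an interval, which is itself descriptive and which the SAP already gives for its odds ratios.

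The person-time rate also has a sound purpose: a simple patient percentage does not allow for lost recording time. That too stands, and it is why the two measures belong side by side.

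Four stronger readings are tempting, and the documents do not support them.

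- *That the SAP assumes independent events.* It gives no variance, so it states no such assumption. The assumption would enter only with a Poisson interval, which nobody has planned. Nor do the documents say how a continuous AV block is counted.
- *That the ratio is the only between-arm view of the primary outcome.* SAP 6.1 and 11.4.1 also plan time-to-last-event with quartiles and Kaplan-Meier curves by treatment, where each patient contributes one time. SAP 11.5.1 counts patients with treatment-emergent events by MedDRA term. These give some patient-level information, but they neither quantify uncertainty in the ratio nor tabulate the percentage for the primary composite.
- *That ratios for rare single types such as ventricular fibrillation will often be undefined.* For separate types, SAP 11.4.1 repeats the counts and rates; it does not clearly plan a ratio.
- *That no output will ever show dispersion.* Table detail is left to shells that are not part of these documents, and listings will show individual data. Only the SAP text can be judged.

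**Conclusion.** The gap is real: the SAP swapped a measure that repeats cannot inflate for one that they can, for a reason unrelated to repeats, and left its main contrast without an interval or a per-patient view. The one-patient examples are plain arithmetic and need only the planned arm size of 20 and an illustrative event pattern.

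The simulated frequencies rest wholly on assumed event rates and repeat patterns. They fall markedly if about 40 patients per arm contribute recordings, and a good part of the instability comes from small arms alone. The harm is a possible misreading of a safety signal and a missing input for pivotal planning. This is a cheap improvement that should be made; it does not invalidate the study.

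**What to change.** In SAP 11.4.1, 11.4.3 and 13:

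1. Beside the person-time rate, report the protocol's percentage of patients with at least one event, with an exact 95% confidence interval for each arm.
2. Give each rate ratio a descriptive 95% interval with the patient as the unit: a negative binomial model with log recorded hours as offset, or a permutation-based interval. Do not use a plain Poisson interval. If a bootstrap is used, state that it undercovers in arms of this size. Report the ratio as not estimable when placebo has no event.
3. Tabulate events per patient by arm, the estimated dispersion, and the ratio without the highest-count patient.
4. State that the intervals are descriptive and that no hypothesis is tested.

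The cost is SAP wording and some programming; no new data or visits are needed. The downside is that wide intervals will be shown.
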